8.1.1 Definition of Adverse Events (AE)

Adverse Event (AE): Any untoward or unfavorable medical occurrence in a human subject, including any abnormal sign (for example, abnormal physical exam or laboratory finding), symptom, or disease, temporally associated with the subject's participation in the research, whether or not considered related to the subject's participation in the research.

8.1.2 Definition of Serious Adverse Events (SAE)

Serious Adverse Event (SAE): Any event temporally associated with the subject's participation in research that meets any of the following criteria:

1. Results in death
2. Is life threatening
3. Requires hospitalization/prolongation of hospitalization
4. Results in congenital anomaly
5. Results in persistent or significant disability/incapacity
6. Required intervention to prevent permanent impairment/damage

8.1.3 Definition of Unanticipated Problems (UP)

Any incident, experience, or outcome (including data loss) that is unexpected (in terms of nature, severity, or frequency) given (a) the research procedures described in the protocol and the characteristics of the subject population being studied. Unanticipated problems may include protocol deviations that are not adverse events

8.2 Classification of an Adverse Event

The Investigator will promptly review documented adverse events and abnormal findings to determine 1) if the abnormal finding should be classified as an adverse event; 2) if there is a reasonable possibility that the adverse event was caused by the study device(s); and 3) if the adverse event meets the criteria for a serious adverse event.

8.2.2 Relationship to Study device

Clinical Trial to improve the magnetic levator prosthesis (MLP) including the development and testing of a novel adjustable force system and comparison to the Kinesio Tape frontalis sling (KTFS) Version 1

If an adverse event or serious adverse event is recorded the study PI will determine the relationship to the study device.

8.3 Time Period and Frequency for Event Assessment and Follow-Up

Adverse events or abnormal findings thought to be associated with the study device will be followed until the event (or its sequel) or the abnormal finding resolves or stabilizes at a level acceptable to the Investigator. Events that have not resolved or stabilized will be followed for 30 days post study completion. Subjects will be encouraged to follow up with their physician for the treatment of any events beyond 30 days post study completion.

8.4 Reporting Procedures

8.4.1 Adverse Event Reporting

All adverse events will be reviewed by the principal investigator within 24 hours of notification and reported to the Mass Eye and Ear IRB on the following schedule:

7. Possibly, Probably, or Definitely Related Expected AE – Report to IRB on annual basis
8. Possibly, Probably, or Definitely Related Expected Serious AE – Report to IRB within 7 days
9. Possibly, Probably, or Definitely Related Unexpected AE – Report to IRB within 30 days of event
10. Possibly, Probably, or Definitely Related Unanticipated Problem – Report to IRB within 7 days of event (24 hours for death or data loss)
11. Possibly, Probably, or Definitely Related Unexpected Serious AE – Report to IRB within 7 days of event (24 hours for death)

8.4.2 Serious Adverse Event Reporting

Any adverse events that are serious, unexpected and related or possibly related to the study will be reported to the Mass Eye and Ear IRB within 7 calendar days from the time the PI becomes aware of the event. Any unexpected and study-related death will be reported to the Mass Eye and Ear IRB within 24 hours of the PI's knowledge of the event by e-mail or telephone.

8.4.3 Unanticipated Problem Reporting

All UAPs involving risks to subjects or others will be reported in writing to the Mass Eye and Ear IRB within 7 calendar days from the time the PI becomes aware of the event. If a UAP or an unexpected SAE results in a subject's death or was potentially life-threatening, the PI will notify the Mass Eye and Ear IRB through e-mail or phone within 24 hours from the time the event is identified. A follow-up report will be submitted if applicable, at a later date when more information is available. For UAPs that result in data loss the PI will notify the Mass Eye and Ear IRB through e-mail or phone within 24 hours from the time the UAP is identified.

10 STATISTICAL CONSIDERATIONS

10.1 Statistical and Analytical Plans

Statistical analysis plans are summarized in the subsequent sections.

10.2 Statistical Hypotheses

Primary outcome measure:

Statistics for the participant characteristics will be presented in terms of mean \pm standard deviation or median \pm interquartile range (25th to 75th). Within subjects repeated measurements, linear mixed effects regression will be used to determine the effect of treatment condition on the IPF values (spontaneous and resting state open), with a random intercept for the subject factor. Subject age, gender, blink sequence (the order of the blink recorded in the video), and the order of interventions (whether evaluated in the first or the second arm of the crossover) will be covariates of interest. Effect of each covariate will be investigated alone, and only statistically significant ($P < .05$) covariates will be included in the final regression model, from which, the estimated marginal means and their 95% confidence interval (CIs) will be reported for each of the outcomes. Missing values at the T2 time point will be imputed from another time point within the same subject (T1 by default or T0 if both T1 and T2 were not available). For volitional blinks, a test of proportionality will be performed to determine the effect of the 3 treatments on the probability of eye not fully closing.

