5 STUDY RECRUITMENT, ENROLLMENT AND WITHDRAWAL

Patient Gateway for recruitment will be utilized.

5.1 Participant Inclusion Criteria:

1. Presence of Blepharoptosis for at least one eye which occludes the visual axis in the resting state (no frontalis drive),
2. Moderate cognitive function or better defined as greater than or equal to 18 out of 30 on a pre-screening of the Mini-Mental State Exam.

3. Age 5 or older. (Children need to be included because they represent an important target population (pediatric neuro-muscular conditions), and because facial structure and skin characteristics may result in a different response than adults)

5.2 Participant Exclusion Criteria:

1. Absence of ptosis which occludes the visual axis
2. Presence of a corneal ulcer of any size, unless managed with a protective contact lens or other method and permission is granted from the candidate's managing eye doctor.
3. Age less than 5,
4. Severe Cognitive impairment defined as MMSE score <18, behaviors consistent with delirium (combinations of disorientation, hallucinations, delusions, and incoherent speech), or lethargy.
5. Presence of corneal hypoesthesia unless cleared for enrollment by a cornea or contact lens specialist;
6. Orbicularis weakness on the side of the ptosis.
7. Mechanical ptosis, including ptosis due to orbital or lid tumor, cicatricial processes affecting the movements of the upper lid, and exophthalmos.
8. Previous ptosis surgery less than 3 months prior to Visit 1.
9. Lid position affected by lid or conjunctival scarring.
10. History of herpes keratitis.
11. Periocular neurotoxin (eg, Botox, Xeomin, Dysport, Myobloc) injections on the side of the ptosis within 3 months prior to Visit 1 and during the study.
12. History of hyperthyroidism or thyroid eye disease (ie, exophthalmos, upper eyelid retraction, diplopia secondary to extraocular muscle involvement). Hypothyroidism that is controlled on medication is allowed.

Hypoesthesia and chronic corneal ulcers may be treated successfully, usually with artificial tears and/or a protective contact lens. Therefore, when there is hypoesthesia or chronic epithelial defect the PI will contact the candidate's cornea or contact lens specialist (e.g. via email or EMR message (EPIC)), and request permission to enroll the candidate. If they do not have a cornea or contact lens specialist, a consult with one at MEE who is not affiliated with the study will be requested prior to enrollment.

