7.3.2 CROSSOVER

After consent and enrollment, subjects will be randomly assigned to one of the two arms for the crossover period. In one arm subjects will receive the MLP first and the KTFS second. In the other arm, subjects will receive the KTFS first and the MLP second.

Each period of the crossover will last for about three weeks, including about two weeks of training in how to apply and remove the device followed by about one week of using the device at home. Training will be conducted at study visits at Mass Eye and Ear. Typically there will be two training visits. Baseline measures of eye lid blinking without and with the device will be taken during training. For the MLP, two baseline measures of eye lid blinking will be recorded one with the real MLP device and one with a sham MLP device to determine how much improvement might occur simply through a placebo effect. However, for the KTFS it will not be possible to take a baseline measure with a sham KTFS. Only subjects and caregivers who demonstrate sufficient ability to apply and remove the device will be permitted to take it home. During the period of home wear, there will be a video call every other day to monitor the subject’s use of the device and safety. During the kfts arm, an occupational or physical therapist consulting with the Massachusetts eye and ear study team may talk with the subject during the video conference call to ensure that the kinesio tape is in the correct position. Mass General Brigham approved software will be used for video calls. During the trial week of home use of devices, subjects will

also receive REDCap survey link notifications each day to complete a brief survey to log if they are wearing the device (see the detailed plan above, and see attached document for survey language and questions).

To ensure no carry-over effects, there will be a washout of about 2 weeks duration between the first and second period of the crossover during which subjects will not be permitted to use any device for their blepharoptosis. (This will be similar to their habitual state before enrollment since none of the participants would have been using any device for their blepharoptosis about two weeks before enrollment).

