10.4.2 Analysis of the Primary Efficacy Endpoint(s)

We will use a repeated measures mixed effects model for analysis of the primary outcome measure (change in interpalpebral fissure during opening and spontaneous blinking). The model will include a random subject-level intercept and a fixed treatment effect (MLP or KTFS). A repeated measures model will be used with primary timepoint for analysis being after 1 week of use. . The model will also include fixed effects of treatment order (i.e., MLP: KTFS vs KTFS:MLP), and crossover period (period 1 or 2), and will control for age and sham opening interpalpebral fissure.

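### Sections 10.2 and 10.4.2 give different models for the primary outcome; if 10.2 treats a sham or no-device reference as a treatment level, that reference enters the standard error of MLP minus KTFS

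*Combined protocol and SAP*

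**What the plan says.** Two sections describe the analysis of the primary outcome.

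- **Section 10.2**, under its primary-outcome label, states that "linear mixed effects regression will be used to determine the effect of treatment condition on the IPF values", "with a random intercept for the subject factor". The response is the IPF value, not its change. The levels of treatment condition are not listed, and no residual covariance structure is given. Covariates, including the order of the blink in the video, are kept only if significant on their own. The paragraph ends with a test for volitional blinks of "the effect of the 3 treatments on the probability of eye not fully closing".
- **Section 10.4.2** models change in IPF with "a random subject-level intercept and a fixed treatment effect (MLP or KTFS"). It adds fixed effects of treatment order and period, and adjusts for age and sham opening IPF.

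Only two treatments are randomised, so the third in 10.2 would be a reference. Section 7.3.2 offers two candidates. One is no device: "Baseline measures of eye lid blinking without and with the device will be taken during training". The other is sham, because the MLP baseline has two recordings, "one with the real MLP device and one with a sham MLP device". Section 5.1 requires "Presence of Blepharoptosis for at least one eye which occludes the visual axis in the resting state", but no IPF mean, SD or correlation is given for any condition.

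**The concern.** The two models can give different standard errors, P values and confidence intervals for the same randomised contrast, and the plan does not say which one decides the trial. The choice could therefore be made after the data are seen.

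The 10.2 model carries a further risk. With a subject intercept as the only random effect, an ordinary fit gives every condition the same variance and every pair of conditions the same correlation. If a reference is one of the levels, its readings help set the residual variance used for MLP minus KTFS, although it is not in that contrast. Eligibility makes it plausible that readings without an active device spread differently from readings with one. A standard error that is too small makes the test liberal; one that is too large wastes power in a trial of 16.

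**Working it through.** **Inputs from the documents.** Final sample size 16, power 0.80, alpha 0.05 (section 10.5); 1 mm difference (section 4.2.1). Variances and correlations are not given and are assumptions below.

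**The plan's own figure.** N = 16 cannot be reproduced without an SD. By two-sided paired t, 80% power at n = 16 needs a mean difference of 0.75 SDs of the within-person difference. If the target is 1 mm, that SD is 1/0.75 = 1.33 mm.

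**Formula.** Take complete data with one value per person per condition. The random-intercept model gives SE(MLP − KTFS) = √(2·MSE/n), where E[MSE] is half the mean of the three pairwise difference variances. The true SE is √(Var(MLP − KTFS)/n). So

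ratio = √(mean of the three pairwise difference variances ÷ Var(MLP − KTFS)).

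Two of the three pairs involve the reference.

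**Case A: equal covariances, device residual SD 1, reference residual SD r.** Var(MLP − KTFS) = 2 and the other two variances are 1 + r², so the ratio is √((2 + r²)/3). Type I error is simulated at n = 16 with 40,000 trials per setting.

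| r | Ratio | Type I error |
|---|---|---|
| 1 | 1.00 | 0.049 |
| 0.75 | 0.92 | 0.071 |
| 0.5 | 0.87 | 0.089 |
| 0.33 | 0.84 | 0.098 |
| 0.25 | 0.83 | 0.103 |

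**Case A with a device response of SD s shared by both devices.** The ratio becomes √((2 + r² + s²)/3). With r = 0.5:

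- s = 1.5: √(4.5/3) = 1.22, and power falls from 0.80 to 0.69.
- s = 2: √(6.25/3) = 1.44, and power falls to 0.53.

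**Case B: the reference's total spread is small.** Case A shrinks only the reference residual. With between-person SD 1, its r = 0.25 still means a total reference SD of √1.0625/√2 = 0.73 of the device SD. Now let the total device SD be 1, the MLP–KTFS correlation ρ, the total reference SD q and its correlation with each device c:

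ratio = √{[(1 − ρ) + (1 + q² − 2cq)] ÷ [3(1 − ρ)]}.

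With q = 0.25:

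| ρ | c | Ratio | Type I error |
|---|---|---|---|
| 0.2 | 0.3 | 0.85 | 0.096 |
| 0.5 | 0 | 1.02 | 0.048 |
| 0.5 | 0.3 | 0.97 | 0.056 |
| 0.5 | 0.5 | 0.94 | 0.064 |
| 0.7 | 0.3 | 1.16 | not simulated |
| 0.9 | 0.3 | 1.84 | not simulated |

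At ρ = 0.8 and c = 0.3 the simulated type I error is 0.011. The bias can go either way and nearly vanishes near ρ = 0.5.

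**Two devices only.** With one row per person per condition, paired type I error is 0.049 to 0.052 in these settings, and the two-level mixed-model SE equals the paired SE (ratio 0.999).

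**Several blinks per person and condition.** The blink-order covariate in 10.2 suggests this. Assume 3 to 10 blinks per condition and a subject-by-device SD of 0.3 to 1.0 of the blink SD. A two-level model with only a subject intercept then has a ratio of 0.36 to 0.90 and type I error of 0.08 to 0.48. Dropping the reference rows is therefore not enough when single blinks are the rows.

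**The case against.** A reader might infer that 10.2 definitely fits three conditions, and that a nearly closed reference lid makes the standard error wrong and the test liberal. The documents do not support that.

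- The count of three appears only in the volitional-blink sentence. A reference level is not needed to reach the endpoint: with a common reference, (MLP − ref) − (KTFS − ref) = MLP − KTFS, so a two-level model of values can estimate the difference in change.
- One residual variance is the usual default for such a fit, not plan text.
- Section 5.1 describes occlusion of the visual axis at rest without frontalis drive. It gives no opening in millimetres and no spread. In spontaneous blinking, readings with a device may also approach closure, so greater device variance cannot be presumed.
- If the reference loses between-person spread as well, case B shows little or no bias at ρ = 0.5.

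Section 10.4.2 is also headed as the primary efficacy analysis and already has two levels. If it governs, the reference mechanism is absent.

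All of this stands against the stronger reading. It does not settle which model governs: 10.2 carries a primary-outcome label too, leaves its levels open, and nothing ranks the two sections.

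**Conclusion.** The point holds as a conflict between two primary models with a conditional consequence. If the 10.2 factor includes a sham or no-device level and the model is fitted in the ordinary way, the standard error of MLP minus KTFS rests partly on a condition outside the randomised contrast. With n = 16 and one value per person per condition, the ratio to the true standard error is about 0.83 (type I error about 0.10) at one end of the assumed range, about 1 in the middle, and 1.4 or more at the other, where power can fall to about 0.53. These figures rest on assumed variances and correlations, so neither the direction nor the presence of a material error can be claimed. Uncertainty about which model applies is reason enough to settle it before analysis. If single blinks are analysed, the missing subject-by-condition effect is usually the larger problem, and it exists without any reference condition.

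**What to change.** 1. Name one primary model, make 10.2 and 10.4.2 agree, and list the levels of treatment condition.
2. Estimate MLP minus KTFS from the two device conditions only, as in 10.4.2, using per-person condition means or within-person MLP − KTFS differences with a period effect.
3. If individual blinks are modelled, add a subject-by-condition random effect.
4. Put any sham or no-device contrast in a separate secondary model.
5. If all three conditions must stay in one model, use an unstructured 3×3 within-subject covariance on per-person means and take the contrast from it. This option was not simulated.

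The cost is SAP wording and residual degrees of freedom: (16 − 1) × (3 − 1) = 30 with three pooled conditions, against 15 for paired differences or 14 with a period effect. The critical value is slightly larger. No new data are needed.

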6.1 Study Device Description

Magnetic Levator Prosthesis (MLP):

Neodymium magnet embedded in a glasses frame and a polymer embedded (PDMS) micro-magnet array fitted externally to the upper lid with IV 3000 securement film. The IV 3000 is FDA approved for extended wear on the skin. Tegaderm, which is essentially the same adhesive, is even FDA approved as an eye covering (we used Tegaderm in early studies but switched to IV 3000 for its superior ease of handling based on packaging technique). It generates a strong bond, in a prior study keeping the magnetic array affixed to the eye lid skin for a mean of 6 ± 4 days with good participant reported comfort when used for

Clinical Trial to improve the magnetic levator prosthesis (MLP) including the development and testing of a novel adjustable force system and comparison to the Kinesio Tape frontalis sling (KTFS) Version 1

2 hours per day during rehabilitation therapies. In order to allow doctors and patients to easily adjust the force of the MLP in the interest of maximizing their comfort and blink quality while accommodating variability in ptosis or lid magnet positioning, we propose to further develop and test a novel approach where the force is adjusted by manually rotating the spectacle magnet with a small dial on the side of the spectacle frame. The MLP is FDA exempt as a Class 1 Device. An Investigational Device Exemption (IDE) application was not required in prior studies approved by the MEEI IRB HSC and should not be required in order to carry out this study. MLP status as a device was reviewed extensively by [name] and her team as well as by legal ([name]), last reviewed in fall 2017.

Kinesio Tape Frontalis Sling (KTFS):

Kinesio Tape is FDA registered as a 510K exempt class 1 device, typically used by physical and occupational therapists to support muscular healing and movement. It is sometimes used on the face in cases of facial palsy or on the eye lid to support the lid in cases of severe blepharoptosis. In such cases it may be attached near the lid margin above the lashes extending up to the forehead skin overlying the frontalis muscle. Alternatively it may be a very short piece attached only along the lid skin. The tape is easily removed.

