As a backup plan in case scheduling constraints mean that it is not possible to schedule a taping visit with the PT:

1. The PI will perform the tape placement.
2. The PI or the research staff will be in attendance as the participants practice placing the tape.
3. The entire process will be recorded and the video loaded onto a secure server or shared via Institutional DropBox
4. The PT will be responsible for reviewing the videos within two days of placement, to ensure proper technique.

Randomization

Participants will be assigned to one of two possible treatment allocations: 1) MLP then KTFS or 2) KTFS then MLP. The allocation will be performed using software that implements the process of minimization. The first participant will be assigned randomly with each subsequent participant assigned in such a way as to approximately balance the number of participants who are 65 years of age and over and who have acute vs chronic ptosis. We propose to balance for these two factors because adults over the age of 65 typically have thinner and looser eyelid skin, and participants with acute ptosis may recover while enrolled in the study, which may affect outcomes. Letter codes, randomly assigned to each of the treatment allocations by a researcher external to the study will be used by the software. The code breaker will be kept in a sealed envelope in a location known only to the external researcher. Data provided to the masked data assessors and the masked person conducting statistical analyses will use the letter codes to identify treatment allocation.

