13.4 PARTICIPANT AND DATA CONFIDENTIALITY

Safeguards will be employed to protect the confidentiality of participant data including the following: Each member of the study team has completed privacy training and information security training at Mass Eye and Ear, paper files will be locked in cabinets when not in use, paper files will be protected from inappropriate access when in use, mobile computing devices and storage media will be locked in cabinets when not in use, computing devices will be protected from inappropriate access when in use, research data will be coded using a study identification number that does not include the participant's initials and is not derived from the participant's identifiable information, the key linking the study ID to the participant's info is available only to the study team, the key will be stored in a locked password protected network with access limited to the study members who require access to this information, electronic data will be stored on folders only available to the study team. Devices for video recording components of the study will be encrypted and/or password protected where possible and data will be promptly transferred and deleted from the device. All video/image and other data will be de-identified prior to publication. We will attempt to capture video/image data so as to only include the eyes, which will therefore not be identifiable. In situations where this is not possible (ie participant moves), video/image data will be cropped to reduce the image to eliminate other facial features. Audio

will ultimately be removed from the video files, but may be needed during processing to determine if blinks are reflexive or the experimenter has asked the participant to volitionally blink. De-identified cropped videos with sound removed will be published as supplementary data or on a public site such as YouTube, and will be used in lectures presenting results of the work. Participants will be informed that their de-identified video recordings may be shared in this manner and ask to check a box on the consent form. Those who decline will not be excluded from participation and this will be emphasized in the consent form and verbally by the PI during the consent process.

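### If spontaneous blinks are analysed one row each, a subject intercept alone understates the standard error and P value of the MLP-KTFS contrast whenever a recording holds several blinks that share variation; sections 10.2 and 10.4.2 do not state the unit of analysis

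*Combined protocol and SAP*

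**What the plan says.** Section 10.2 describes a linear mixed model "on the IPF values (spontaneous and resting state open), with a random intercept for the subject factor". That intercept is its only random term. Among the candidate covariates is "blink sequence (the order of the blink recorded in the video". Each covariate is first tested alone and kept only if significant.

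Section 10.4.2 describes the primary analysis again: "The model will include a random subject-level intercept and a fixed treatment effect (MLP or KTFS"). It adds treatment order, period, age and sham opening fissure. On the repeated measurements it says only: "A repeated measures model will be used with primary timepoint for analysis being after 1 week of use". Blink order is not listed, no residual covariance is named, and the text does not say how blinks are turned into the change that is analysed.

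Section 10.4.1 takes the measurements from video at several timepoints but gives no averaging rule and no number of blinks per recording. Section 13.4 says that audio "may be needed during processing to determine if blinks are reflexive or the experimenter has asked the participant to volitionally blink". This suggests that a recording can hold several blinks, but it does not settle what a row is. Section 10.4.3 sends volitional fissure change through the same approach as the primary outcome.

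**The concern.** Blink order can vary only if rows are individual blinks, and testing it alone already needs a blink-level dataset. For spontaneous blinks, section 10.2 therefore points to blink rows with a subject intercept.

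The subject intercept cancels from a within-subject device contrast. What remains in the contrast is whatever all blinks of one recording have in common: how the device sat that day, the state of the ptosis, or a subject's own response to that device. An intercept-only model treats those blinks as independent given the subject. It therefore tests the contrast against a residual made up mostly of blink-to-blink noise. A fixed period effect removes only the average shift between periods, not differences between subjects in that shift.

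The documents allow for such variation. Section 6.1 motivates the adjustment dial as a way of "while accommodating variability in ptosis or lid magnet positioning", and section 10.6.1 notes that "participants with acute ptosis may recover while enrolled in the study, which may affect outcomes". At stake is whether session-to-session variation could be reported as a significant MLP-KTFS difference on the primary outcome, in a trial whose required size is now 16 (section 10.5).

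**Working it through.** **Inputs from the documents.** 16 subjects (10.5); two sequences (10.6.1); a subject intercept only, with period and sequence effects (10.4.2); alpha 0.05 (10.5). The figure of 16 cannot be reproduced, because neither an SD nor a powering effect is given. It is used here only as n.

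**Assumptions, since the documents give no value.** 8 subjects per sequence; one recording per subject and device at the one-week timepoint; m blinks in each; a two-sided test. Within-subject variance is scaled to 1, with a share rho at recording level and 1-rho at blink level.

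**Formulas.** Write B = (1-rho) + m*rho and W = 1-rho.

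- True variance of the device contrast: 2B/(m*n).
- Variance used by the intercept-only model: 2*MSE/(m*n).
- The MSE pools two sources. Between recordings within subject there are 32 - 16 - 2 = 14 df with expectation B (device and period use the 2). Within recordings there are 32(m-1) df with expectation W.
- E[MSE] = [14B + 32(m-1)W] / [14 + 32(m-1)].
- Ratio of true to modelled standard error: about sqrt(B/E[MSE]).

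Age and sham opening fissure, taken as one value per subject, do not change the within-subject residual.

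**Worked cell, m=5, rho 0.3.** B = 0.7 + 1.5 = 2.2 and W = 0.7. Then E[MSE] = (14 x 2.2 + 128 x 0.7)/142 = 120.4/142 = 0.848. The ratio is sqrt(2.2/0.848) = 1.61. The nominal critical value of 1.98 is thus worth about 1.98/1.61 = 1.23 true standard errors, which gives a two-sided error near 22%.

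**Results** (type I error by simulation from these distributions):

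| m | rho | B | E[MSE] | SE ratio | Type I error |
|---|---|---|---|---|---|
| 1 | any | 1.00 | 1.00 | 1.00 | 5% |
| above 1 | 0 | 1.00 | 1.00 | 1.00 | 5% |
| 3 | 0.02 | 1.04 | 0.991 | 1.02 | 5.5% |
| 3 | 0.1 | 1.20 | 0.954 | 1.12 | 8% |
| 10 | 0.05 | 1.45 | 0.973 | 1.22 | 11% |
| 5 | 0.3 | 2.20 | 0.848 | 1.61 | 22% |
| 10 | 0.3 | 3.70 | 0.839 | 2.10 | 35% |

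The coverage of a 95% interval for the difference is 100% minus the last column.

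**Checks.** Direct random-intercept fits to blink rows at m=10, rho 0.2, with period and blink order in the model (300 runs), rejected a true null 26% of the time. Their mean standard error was 0.105, against a true value of sqrt(2 x 2.8/160) = 0.187. Analysing one mean per subject and period gave 4.4% to 5.7% in every setting tried (m from 1 to 20, rho from 0 to 0.5).

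**The case against.** The strongest reply is that m and rho are unknown, so 22% or 35% is no better supported than 5% or 6%. That stands, and is why the table runs down to rho 0.02 and zero. The evidence for rho above zero is also only qualitative. The dial in section 6.1 exists to offset the variability it mentions, section 7.3.2 provides therapist checks of tape position, and section 10.6.1 adds video review of backup taping and minimization on acute versus chronic ptosis. These measures may make rho smaller, but none makes it zero. Minimization balances the sequences; it does not remove variation between recordings of one subject.

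A second reply is that the repeated-measures wording in 10.4.2 could cover a within-recording covariance, or that 10.4.2 may intend one value per recording. Either would remove the problem at the one-week timepoint. Neither is stated, and the blink-order covariate in 10.2 points the other way.

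A third is that section 10.2 promises only that "the estimated marginal means and their 95% confidence interval (CIs) will be reported for each of the outcomes". Intervals for single condition means are indeed little affected: coverage is about 92% to 95% in the two-device cells from m=3, rho 0.1 to m=10, rho 0.3, with between-subject variance 0.25 to 2 times within-subject variance. But 10.2 also sets out to determine the effect of treatment condition, and that test carries the error.

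A reader might also infer that resting opening is scored per blink, or that 16 subjects are too few. The documents support neither. Blink order bears on spontaneous blinks, and 10.5 does not describe the model behind the interim analysis.

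**Conclusion.** The point holds conditionally. Three things must be true together: blink-level rows, more than one blink per recording, and variation shared within a recording. The first is implied by section 10.2 for spontaneous blinks, and the other two are not excluded anywhere. When all three hold, the direction is certain: the standard error and P value of the MLP-KTFS contrast are too small. The size runs from negligible (5.5%) to serious (35%) over the assumed range and cannot be narrowed from the documents.

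It would be tempting to say that the planned primary test has a false-positive rate of 20% or more. The documents do not support that, because they fix neither m nor rho and section 10.4.2 can be read as one value per recording. What is established is that the model as written gives no protection against this variation, and that two sections leave the analyst to choose the unit. It should be fixed before the final analysis, at little cost.

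**What to change.** State the unit of analysis identically in 10.2 and 10.4.2, for spontaneous blinks and for resting opening, and say how the change is formed from the blinks. Then choose one of these:

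- **(a)** Average the blinks to one value per subject and device at the one-week timepoint. Fit the 10.4.2 crossover model to those values (device, period, sequence, age, sham opening fissure, subject intercept) and drop blink order as a covariate.
- **(b)** Keep blink rows and add a subject-by-device random effect to the subject intercept, not in place of it, with Kenward-Roger degrees of freedom. Add a recording effect if several visits are modelled.

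The population includes bilateral ptosis, so also say which eye is used or how two eyes are combined. Apply the same rule to volitional fissure change, since 10.4.3 uses the same approach. The test of incomplete volitional closure is a different analysis and needs its own statement.

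The cost is SAP wording and model syntax, with no new data. The interval for the difference may widen. If rho is in fact zero, option (a) loses only degrees of freedom: at m=3 the t quantile goes from 1.99 (78 df) to 2.14 (14 df), an interval about 8% wider.
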